5.3. Lifestyle Considerations

5.3.1. Meals and Dietary Restrictions

Participants will refrain from consuming Seville oranges, pomegranates, grapefruit, pomelos, exotic citrus fruits, grapefruit hybrids, and juice containing these restricted fruits from 72 hours before the first dose of study drug and throughout the study.

5.4. Screen Failures

Screen failures are defined as participants who consent to participate in the clinical study but are not subsequently entered in the study. This could be because the participant does not meet the eligibility criteria as described in Section 5.1 and Section 5.2 or for any other reason. At a minimum, the following information must be collected and entered into the eCRF: demography, screen failure details, and eligibility criteria. Information on SAEs that occur after consent should be submitted to the sponsor.

Individuals who do not meet the criteria for participation in this study (screen failure) may be rescreened 1 time.

Tests with results that fail eligibility requirements may be repeated once during screening if the investigator believes the result to be in error. Additionally, a participant who fails screening may

repeat the screening process 1 time if the investigator believes that there has been a change in eligibility status. Participants who rescreen must reconsent and be assigned a new participant number.

5.5. Replacement of Participants

No participants will be replaced at any time during this study.

5.6. Data Monitoring Committee

This study will use a DMC to monitor safety at the planned analyses. The DMC will make recommendations to the Sponsor clinical team regarding steps to ensure both participant safety and the continued ethical integrity of the trial. Also, the DMC may review interim trial results (see Section 10.5), consider the overall risk and benefit to trial participants, and recommend if the trial should continue in accordance with the Protocol. Specific details regarding composition, responsibilities, and governance, including the roles and responsibilities of the members are described in the DMC charter. Requirements for and proper documentation of DMC reports, minutes, and recommendations are also described in the DMC charter. The DMC charter will be reviewed and approved by all the DMC members.

6. STUDY TREATMENT

6.1. Study Treatment Administered

Table 9 presents the study treatment information. See Appendix C for instructions for participant handling of study drug.

Table 9: Study Treatment Information

Study treatment name:	INCB086550
Mechanism of action:	PD-L1 inhibitor
Dosage formulation:	Tablet
Unit dose strength/ dosage level:	100 mg and 400 mg
Route of administration:	Oral
Administration instructions	
Administered orally in 100 mg or 400 mg tablets.Study drug may be taken QD or BID on the days specified of a 21-day or 28 day cycle for a given dose level.
QD doses are taken in the morningBID doses are taken in the morning and evening approximately 12 hours apart. If the morning or evening dose is missed by more than 4 hours, then that dose should be skipped, and the next scheduled dose should be taken at the usual time.INCB086550 should be administered with water.Participants should fast for at least 2 hours before and at least 1 hour after each dose. INCB086550 tablets may be crushed and administered with water, apple juice, applesauce, or yogurt. Instructions for this administration are detailed in the Pharmacy Manual.
Packaging and labeling:	INCB086550 will be provided as 35 tablets per bottle. Each container will be labeled as required per country requirements.
Storage:	Must be refrigerated and protected from light. Store at 2°C-8°C (36°F-46°F).
Status of treatment in participating countries:	Investigational

6.2. Preparation, Handling, and Accountability

The investigator or designee must confirm appropriate temperature conditions have been maintained during transit for all study treatments received and any discrepancies are reported and resolved before use of the study treatment.

Only participants enrolled in the study may receive study treatment, and only authorized site staff may supply or administer study treatment. All study treatment must be stored in a secure, environmentally controlled, and monitored (manual or automated) area in accordance with the labeled storage conditions with access limited to the investigator and authorized site staff.

The investigator (or designee) is responsible for study treatment accountability, reconciliation, and record maintenance (ie, receipt, reconciliation, and final disposition records). Inventory and accountability records must be maintained and readily available for inspection by the study monitor and are open to inspection at any time by any applicable regulatory authorities. The investigator or designee must maintain records that document:

- Delivery of study drug to the study site.
- Inventory of study drug at the site.
- Participant use of the study drug including tablet counts from each supply dispensed.
- Return of study drug to the investigator or designee by participants.

The investigational product must be used only in accordance with the Protocol. The investigator will also maintain records adequately documenting that the participants were provided the specified study drug. These records should include dates, quantities, and any available batch or serial numbers or unique code numbers assigned to the investigational product and study participants.

Completed accountability records will be archived by the site. The investigator or designee will be expected to collect and retain all used, unused, and partially used containers of study drug until verified by the study monitor (unless otherwise agreed to by the sponsor). At the conclusion of the study, the investigator or designee will oversee shipment of any remaining study drug back to the sponsor or its designee for destruction according to institutional SOPs. If local procedures mandate on-site destruction of investigational supply, the site should (where local procedures allow) maintain the investigational supply until the study monitor inspects the accountability records in order to evaluate compliance and accuracy of accountability by the investigative site. At sites where the study drug is destroyed before monitor inspection, the monitors rely on documentation of destruction per the site SOP.

Further guidance and information for the final disposition of unused study treatments are provided in the Study Reference Manual.

6.3. Measures to Minimize Bias: Randomization and Blinding

All participants will be centrally assigned to open-label study treatment using IRT. Full details will be provided in the IRT Study Reference Manual. Study drug will be dispensed at the study visits summarized in the SoA (see [Table 3](#), [Table 4](#), [Table 5](#), and [Table 6](#)). Returned study drug should not be redispatched to the participants.

6.4. Study Treatment Compliance

Compliance with all study-related treatments should be emphasized to the participant by the site personnel, and appropriate steps should be taken to optimize compliance during the study. Compliance with INCB086550 will be calculated by the sponsor based on the drug accountability (eg, tablet counts) documented by the site staff and monitored by the sponsor/designee. Participants will be instructed to bring all unused study drug with them to the study visits in order for site personnel to conduct tablet counts to assess study drug accountability. The drug accountability documentation will be used by the sponsor to calculate treatment compliance.

6.5. Dose Modifications

Interruptions and modifications to the study treatment regimen are allowed per Protocol. The occurrence of toxicities (related or unrelated to study drug) will guide decisions for treatment interruptions, modifications, or discontinuation for individual participants.

Investigators should contact and discuss dose modifications with the medical monitor.

Intraparticipant dose escalations will not be permitted during the course of the study.

6.5.1. Management of Immune-Related Adverse Events

An AE of a potential immunologic etiology or an irAE may be defined as an AE consistent with an immune phenomenon associated with drug exposure after all other etiologies have been eliminated. Immune-related AEs may be expected based on the nature of INCB086550, its mechanism of action, and reported experience with other immunotherapies. If an irAE is suspected, efforts should be made to rule out neoplastic, infectious, metabolic, autoimmune, toxic, or other etiologic causes before categorizing an AE as an irAE. The investigator should promptly notify the sponsor (or designee) about participants who develop an irAE \geq Grade 2.

Participants, who have irAEs that resolve to \leq Grade 1 within 14 days, may be rechallenged at the starting dose or with a dose reduction. Continuation, withholding, dose modification, or discontinuation of INCB086550 will depend on severity of the irAE and affected organ/organ system and should be discussed with the medical monitor. Any irAEs \geq Grade 3 that require permanent discontinuation of INCB086550 per [Table 10](#) may only be rechallenged with approval of the medical monitor. Elevations in amylase or lipase that are \geq Grade 3 do not require dose interruption or reduction if the participant is asymptomatic or if the elevation is clinically insignificant and has been discussed with the medical monitor.

Participants should receive appropriate supportive care measures as deemed necessary by the treating investigator. Suggested measures for the management of irAEs are outlined in [Table 10](#). For each AE, attempts should be made to rule out other causes, including but not limited to metastatic disease, bacterial infection, or viral infection that might require specific supportive care.

Management guidance for irAEs not detailed elsewhere in the Protocol should follow the ASCO Clinical Practice Guideline or ESMO Clinical Practice Guidelines ([Brahmer et al 2018](#), [Haanen et al 2017](#)).

Table 10: Immune-Related Adverse Events Management Guidelines for INCB086550

irAE	CTCAE v5 Grade	Guidance for Restarting INCB086550	Monitoring and/or Supportive Care
Pneumonitis	Grade 1	
Continue INCB086550 if asymptomatic.
 
Withhold INCB086550 given radiographic evidence of pneumonitis progression. May resume with radiographic evidence of improvement or resolution.
	
 Monitor as appropriate (CT, spirometry/DLCO, history and physical examination, pulse oximetry, chest x-ray). If no improvement, treat as Grade 2.
	Grade 2	Withhold INCB086550 until resolution to \leq Grade 1.	
 Administer systemic corticosteroid (prednisone 1-2 mg/kg or equivalent) with taper. May consider empiric antibiotics. Consider bronchoscopy with bronchoalveolar lavage. Monitor as appropriate (history and physical examination, pulse oximetry, chest x-ray). If no improvement within 2-3 days, treat as Grade 3.
	Grade 3, Grade 4, or recurrent Grade 2	Permanently discontinue INCB086550.	
 Administer IV methylprednisolone 1-2 mg/kg or equivalent with taper. Administer empiric antibiotics. If no improvement after 2 days, may add infliximab 5 mg/kg, mycophenolate mofetil IV 1 g twice daily, IV immunoglobulin for 5 days, or cyclophosphamide. Pulmonary and infectious disease consults, if necessary. Bronchoscopy with bronchoalveolar lavage \pm transbronchial biopsy. 
Note: If clinical presentation is consistent with pneumonitis, transbronchial biopsy is not needed.

Table 10: Immune-Related Adverse Events Management Guidelines for INCB086550 (Continued)

irAE	CTCAE v5 Grade	Guidance for Restarting INCB086550	Monitoring and/or Supportive Care
Diarrhea/colitis	Grade 1	Continue INCB086550.	
 Monitor as appropriate. Provide supportive care (hydration, electrolyte replacement, dietary changes). Consider gastroenterology consult for prolonged event.
	Grade 2 or Grade 3	Withhold INCB086550 until resolution to \leq Grade 1.	Grade 2: 
 If clinically indicated, administer systemic corticosteroids (prednisone 1 mg/kg or equivalent) with taper. Consider symptomatic treatment with antidiarrheal if infection has been ruled out. Grade 3: 
 Administer systemic corticosteroids (prednisone 1-2 mg/kg or equivalent) with taper. If no improvement after 3-5 days, IV corticosteroid with taper or infliximab. Gastroenterology consult for additional workup as appropriate.
	Grade 4	Permanently discontinue INCB086550.	
 Administer IV methylprednisolone 1-2 mg/kg or equivalent with taper. If no improvement after 2-3 days, consider infliximab 5-10 mg/kg. Gastroenterology consult for additional workup as appropriate.

Table 10: Immune-Related Adverse Events Management Guidelines for INCB086550 (Continued)

irAE	CTCAE v5 Grade	Guidance for Restarting INCB086550	Monitoring and/or Supportive Care
Hepatitis (AST/ALT increased and/or total bilirubin increased)	Grade 1	Continue INCB086550.	
 Repeat laboratory measurements 1-2 times/week until return to baseline. Provide supportive care for symptoms.
	Grade 2 or Grade 3 lasting \leq 10 days	Withhold INCB086550 until resolution to \leq Grade 1.	
 Repeat laboratory measurements every 3 days until return to baseline. If elevations persist after 3 days or symptomatic, administer systemic corticosteroids (prednisone 0.5-1 mg/kg or equivalent) with taper. Infliximab should NOT be used.
	Grade 3 lasting > 10 days or Grade 4	Permanently discontinue INCB086550.	
 Repeat laboratory measurements every 1-2 days until return to baseline. Administer IV methylprednisolone 1-2 mg/kg or equivalent with taper. If corticosteroid refractory or elevations persist after 3 days, consider mycophenolate mofetil or azathioprine. Infliximab should NOT be used. Hepatology consult for additional workup, as appropriate.
Dermatitis	Grade 1 or Grade 2	Continue INCB086550.	
 Consider dermatology consult. Supportive care with topical emollients, oral antihistamines. Administer topical corticosteroid as needed. If no improvement with topical corticosteroid, consider systemic (oral) corticosteroid.
	Grade 3	Withhold INCB086550 until resolution to \leq Grade 1.	
 Dermatology consult. Administer IV methylprednisolone 1-2 mg/kg or equivalent with taper.
	Grade 4	Permanently discontinue INCB086550.	
 Monitor for progression to severe cutaneous adverse reaction (eg, Stevens-Johnson syndrome, toxic epidermal necrolysis, drug reaction with eosinophilia and systemic symptoms/drug-induced hypersensitivity syndrome).
Nephritis or renal dysfunction (creatinine increased)	See Table 12 for immune-related nephritis and renal dysfunction AE management guidelines.		

Table 10: Immune-Related Adverse Events Management Guidelines for INCB086550 (Continued)

irAE	CTCAE v5 Grade	Guidance for Restarting INCB086550	Monitoring and/or Supportive Care
Diabetes mellitus	Grade 1 or Grade 2	Continue INCB086550.	
 Endocrine consult, especially for Type 1 diabetes mellitus. Oral antihyperglycemic therapy ± insulin for new onset Type 2 diabetes mellitus, as appropriate. Insulin for Type 1 diabetes mellitus. Titrate therapy to achieve glucose control.
	Grade 3 or Grade 4	Withhold INCB086550 until glucose control is achieved and \leq Grade 1.	
Hypothyroidism	Grade 1	Continue INCB086550.	
 Monitor TSH, FT4 as appropriate.
	Grade 2	Consider withholding until resolution to \leq Grade 1.	
 Endocrine consult for Grade 3 or Grade 4, consider for Grade 2. Thyroid hormone replacement as appropriate. Monitor TSH, FT4 while titrating hormone replacement and once adequately resolved.
	Grade 3 or Grade 4	Withhold INCB086550 until resolution to \leq Grade 1 with appropriate thyroid hormone supplementation.	
 Monitor TSH, FT4 as appropriate. Consider endocrine consult. Beta-blocker (eg, atenolol, propranolol) for symptomatic relief.
Hyperthyroidism	Grade 1	Continue INCB086550.	
 Endocrine consult. Prednisone 1-2 mg/kg or equivalent with taper only for severe symptoms of concern for thyroid storm. Beta-blocker (eg, atenolol, propranolol) for symptomatic relief. Consider potassium iodide or thionamide (methimazole or propylthiouracil).
	Grade 2	Consider withholding until resolution to \leq Grade 1.	
 Consider endocrine consult. Beta-blocker (eg, atenolol, propranolol) for symptomatic relief.
	Grade 3 or Grade 4	Withhold INCB086550 until resolution to \leq Grade 1 with appropriate therapy.	
 Administer high-dose corticosteroids initiated rapidly (oral or IV depending on symptoms). Manage cardiac symptoms according to American College of Cardiology/American Heart Association. Cardiology consult. May offer immediate transfer to a coronary care unit for participants with elevated troponin or conduction abnormalities. In participants without an immediate response to high-dose corticosteroids, may offer early institution of cardiac transplant rejection doses of corticosteroids (eg, methylprednisolone 1 g every day) and the addition of either mycophenolate, infliximab, or antithymocyte globulin.
Myocarditis	Any Grade	Permanently discontinue INCB086550.	
 Administer high-dose corticosteroids initiated rapidly (oral or IV depending on symptoms). Manage cardiac symptoms according to American College of Cardiology/American Heart Association. Cardiology consult. May offer immediate transfer to a coronary care unit for participants with elevated troponin or conduction abnormalities. In participants without an immediate response to high-dose corticosteroids, may offer early institution of cardiac transplant rejection doses of corticosteroids (eg, methylprednisolone 1 g every day) and the addition of either mycophenolate, infliximab, or antithymocyte globulin.

Table 10: Immune-Related Adverse Events Management Guidelines for INCB086550 (Continued)

irAE	CTCAE v5 Grade	Guidance for Restarting INCB086550	Monitoring and/or Supportive Care
Hypophysitis or adrenal insufficiency	Grade 1 or Grade 2	Consider withholding until resolution to \leq Grade 1.	
 • Endocrine consult. • Administer systemic corticosteroids (with taper) and hormone replacement as clinically indicated.
	Grade 3 or Grade 4	Withhold INCB086550 until resolution to \leq Grade 1.	
Nervous system disorders	Grade 1	Continue INCB086550.	
 • Neurologic consult • Monitor closely for any symptom progression.
	Grade 2	Withhold INCB086550 until resolution to \leq Grade 1.	
 • Neurologic consult and workup including MRI. Consider EMG, lumbar puncture, and CSF analysis. • Administer supportive care and corticosteroids. • Monitor closely for any symptom progression.
	Grade 3	Withhold INCB086550 until resolution to \leq Grade 1 OR Permanently discontinue INCB086550.	
 • Neurologic consult and workup including MRI. Consider EMG, lumbar puncture, and CSF analysis. • Administer supportive care and corticosteroids. • Continuation, withholding, or discontinuation of INCB086550 will depend on severity of irAE and affected organ/organ system. Restarting participants after Grade 3 nervous system AEs requires medical monitor approval.
	Grade 4	Permanently discontinue INCB086550.	
 • Neurologic consult and workup including MRI. Consider EMG, lumbar puncture, and CSF analysis. • Administer supportive care and/or corticosteroids.
Other irAEs	Grade 1	Continue INCB086550.	
 • Administer supportive care and/or corticosteroid for symptoms. • Continuation, withholding, or discontinuation of INCB086550 will depend on severity of irAE and affected organ/organ system. Investigator must discuss with medical monitor. • Consider relevant consults, as appropriate.
	Grade 2	Continue INCB086550 OR withhold INCB086550 until resolution to \leq Grade 1	
	Grade 3	Withhold INCB086550 until resolution to \leq Grade 1	
	Grade 4	Permanently discontinue INCB086550.	

CSF = cerebrospinal fluid; EMG = electromyography; FT4 = free thyroxine; TSH = thyroid-stimulating hormone.

6.5.2. Criteria and Procedures for Dose Interruptions and Adjustments of Study Drug

Dose interruptions and modifications of INCB086550 may occur for participants during the study treatment period. The short half-life of INCB086550 (8.62 hours after a single 100 mg dose) may improve management options for participants who experience irAEs, unobtainable with immune checkpoint monoclonal antibodies, which possess long half-lives. Management guidelines for AEs requiring dose modifications are described for general hematologic and nonhematologic toxicities that are not thought to be immune-related in [Table 11](#). Decisions regarding dose interruptions of INCB086550 should be made using clinical judgment of the investigator, taking into account the possible relatedness of the AE to the study drug and the participant's underlying condition. Adverse events that have a clear alternative explanation or transient (≤ 72 hours) abnormal laboratory values without associated clinically significant signs or symptoms may be exempt from dose-interruption/discontinuation rules. Participants may resume treatment as per management guidelines if no medical condition or other circumstance exists that, in the opinion of the investigator, would make the participant unsuitable for further treatment and participation in the study. Treatment with INCB086550 may be delayed for up to 28 days to allow for resolution of toxicity. The treating investigator should contact the medical monitor to discuss the case of any participant whose treatment has been interrupted for more than 28 days before restarting treatment with INCB086550.

Dose interruptions are permitted in the case of medical/surgical events or logistical reasons not related to study therapy (eg, elective surgery, unrelated medical events, subject vacation, holidays). Participants should be placed back on study therapy within 4 weeks (ie, 28 days) of the scheduled interruption, unless otherwise discussed with the medical monitor. The reason for interruption should be documented accordingly.

Safety concerns should be discussed with the sponsor immediately upon occurrence or awareness to determine if the participant should continue or discontinue study treatment. Additional unscheduled visits with CBC may be performed.

Table 11: Non-Immune-Related Adverse Events Dose Modification Guidelines

CTCAE Severity	Suggested Modification
Hematological toxicities	
CTCAE Grade 1 or Grade 2	Continue INCB086550 treatment at the discretion of the investigator.
CTCAE Grade 3	
 Restart when toxicity resolves to baseline or \leq Grade 1. First occurrence: Restart at same dose or reduce dose by 1 dose level at the discretion of the investigator after discussion with the medical monitor. Second occurrence: Restart at reduced dose (if not already).
CTCAE Grade 4	Permanently discontinue study drug or discuss with medical monitor if treatment algorithm for CTCAE Grade 3 events (above) is appropriate.
Nonhematological toxicities	
All Grades	
 For irAEs, follow the guidelines in Table 10. 
Permanently discontinue treatment for:
 
 Any liver function abnormalities that meet the definition of Hy's law. Encephalopathy of any grade.
CTCAE Grade 1 or 2	
Continue treatment and initiate supportive care at the discretion of the investigator EXCEPT:
 
 Permanently discontinue treatment for \geq Grade 2 ocular toxicity.
CTCAE \geq Grade 3	
Permanently discontinue study treatment for any \geq Grade 3 nonhematologic toxicity EXCEPT:
 
 Transient (\leq 72 hours) abnormal laboratory values without associated clinically significant signs or symptoms. Laboratory abnormalities \geq Grade 3 without associated clinically significant signs or symptoms. Nondesquamating rash \geq Grade 3 that resolves within 48 hours with standard treatment. 
Grade 3 rash in the absence of desquamation, without mucosal involvement, and not requiring systemic steroids that resolves to \leq Grade 1 in \leq 14 days.
 
 Grade 3 fatigue $<$ 1 week. Nausea, vomiting, and diarrhea adequately controlled with medical therapy within 48 hours. 
 For \geq Grade 3 events that do not require permanent discontinuation, the following guidelines should be used: 
 Restart when toxicity resolves to baseline or \leq Grade 1. First occurrence: Restart at same dose or reduce dose by 1 dose level at the discretion of the investigator after discussion with the medical monitor. Second occurrence: Restart at reduced dose (if not already). Third occurrence: Permanently discontinue study drug.

INCB086550 is an inhibitor of the creatinine transporter OCT2 (in vitro IC₅₀ of 2.6 μ M). Creatinine increases observed during treatment with INCB086550 may be due to immune-mediated nephritis, inhibition of the OCT2 transporter, or may be unrelated to drug administration. Work-up should begin early and a nephrology consult considered. Assessment and management of INCB086550 should consider the relative increase in creatinine from baseline, and timing of the increase. Guidelines for continuing or withholding INCB086550 treatment and the timing for repeat chemistry laboratory studies are presented in [Table 12](#).

Table 12: Management and Evaluation of Increased Creatinine

CTCAE v5.0 Grade	Guidance for Restarting INCB086550	Monitoring and/or Supportive Care
Relative increase of 1 CTCAE Grade in Cycle 1 (If baseline was within normal range, a change to Grade 1, or if Grade 1 at baseline, a change to Grade 2).	Continue INCB086550 and recheck chemistry labs in 48 hours. If creatinine is stable and there is no further increase in 48 hours, INCB086550 may be continued and labs checked in 48-72 hours. If creatinine increases within 48 hours, withhold INCB086550 and recheck chemistry labs in 48 hours. INCB086550 treatment may resume when creatinine returns to Grade 1 or baseline.	
 Evaluate for alternative etiologies (eg, IV contrast, fluid status) and recheck labs in 48 hours.
Grade 1 ($> \text{ULN} - 1.5 \times \text{ULN}$)	Continue INCB086550.	
 Evaluate for alternative etiologies (eg, IV contrast, fluid status).
Grade 2 ($> 1.5 \times \text{ULN} - 3.0 \times \text{ULN}$)	If creatinine was Grade 1 at baseline, INCB086550 may be continued and labs checked in 48 hours. If creatinine is stable and there is no further increase in 48 hours, INCB086550 may be continued and labs checked in 48-72 hours. If creatinine increases within 48 hours, withhold INCB086550 and recheck chemistry labs in 48 hours. INCB086550 treatment may resume when creatinine returns to Grade 1 or baseline. If creatinine was within normal range at baseline, withhold INCB086550 until resolution to \leq Grade 1.	
 Consult nephrology. Evaluate for alternative etiologies (eg, IV contrast, fluid status). Administer prednisone 0.5-1 mg/kg or equivalent with appropriate taper.
Grade 3 ($> 3.0 \times \text{ULN} - 6.0 \times \text{ULN}$), Grade 4 ($> 6.0 \times \text{ULN}$), or persistent Grade 2	Permanently discontinue INCB086550.	
 Consult nephrology. Evaluate for alternative etiologies (eg, IV contrast, fluid status). Administer prednisone 1-2 mg/kg or equivalent with appropriate taper. If elevations persist for > 3 days, consider mycophenolate.

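### Table 12's prednisone bullets for Grade 2 and higher creatinine rises carry no condition on cause, and they do not fit the table's own lead-in, its Cycle 1 row, Tables 10 and 11, or the steroid limits in Section 6.6

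*Protocol*

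**What the plan says.** **Lead-in to Table 12 (Protocol Section 6.5.2).** The drug inhibits the OCT2 creatinine transporter, and a rise on treatment "may be due to immune-mediated nephritis, inhibition of the OCT2 transporter, or may be unrelated to drug administration". The lead-in then gives the table's purpose: "Guidelines for continuing or withholding INCB086550 treatment and the timing for repeat chemistry laboratory studies are presented in" Table 12. Steroids are not mentioned there.

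**Table 12 (increased creatinine).** Apart from a first row for early one-grade changes, the rows are set by CTCAE grade; none is set by cause.
- Cycle 1, relative increase of one grade. This includes the case "if Grade 1 at baseline, a change to Grade 2". Supportive care: "Evaluate for alternative etiologies (eg, IV contrast, fluid status) and recheck labs in 48 hours". There is no steroid bullet.
- Grade 1. Evaluation of other causes only.
- Grade 2. Nephrology consult, evaluation of other causes, and "Administer prednisone 0.5-1 mg/kg or equivalent with appropriate taper".
- Grade 3, Grade 4 or persistent Grade 2. Nephrology consult, evaluation of other causes, and "Administer prednisone 1-2 mg/kg or equivalent with appropriate taper".

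**Table 10 (Section 6.5.1).** The nephritis row sends the reader to Table 12 "for immune-related nephritis and renal dysfunction AE management guidelines". The text before Table 10 says "Suggested measures for the management of irAEs are outlined in" that table, and asks that other causes be excluded before an event is classed as an irAE.

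**Table 11 (Section 6.5.2).** For non-immune, nonhematological Grade 1 or 2 events, supportive care is left to the investigator.

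**Sections 6.6.2.4 and 6.6.3.** Systemic steroids are limited to 10 mg/day of prednisone or equivalent. Immunosuppressants are allowed for irAEs handled under Table 10, or as contrast-allergy prophylaxis.

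**The concern.** Two of the three causes named above Table 12 are not immune, yet the two prednisone bullets make no distinction. Work-up for other causes is a parallel bullet in the same cells, and no row says what becomes of the steroid when that work-up finds another explanation.

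A site that follows the cells literally would therefore give immunosuppressive doses for a non-immune rise. A site that reads Table 12 through Table 10 would not. Two sites could treat the same laboratory result differently, and both could point to the protocol. The stake is participant safety, together with uneven conduct between sites.

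**Working it through.** The documents give no figure to reproduce on this point. The check sets the passages side by side.

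**1. Scope of Table 12.** Its title and lead-in cover any creatinine increase during treatment. Table 10 cites it for immune-related renal events only. The two scopes differ, and the steroid bullets do not say which applies.

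**2. Does other text release the steroid bullets for a non-immune rise?**
- Section 6.5.2 allows an exemption for events with a clear alternative explanation, but from the dose-interruption and discontinuation rules only. It does not reach the steroid bullets.
- Section 6.5.1 asks for other causes to be excluded before an event is classed as an irAE. Table 12 does not tie prednisone to that classification.
- The protocol attaches conditions to immunosuppressants elsewhere. In Table 10, the steroid for Grade 2 diarrhea/colitis depends on clinical indication, and the steroid for hepatitis of Grade 2, or Grade 3 lasting up to 10 days, depends on persistence or symptoms. In Table 12 itself, mycophenolate depends on elevation beyond 3 days. The Table 12 prednisone bullets have no such condition.

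**3. A non-immune Grade 2 rise under Tables 11 and 12.** Table 11 leaves supportive care to the investigator. Table 12 lists prednisone. Nothing says which table governs.

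**4. Against the steroid limits.** Take the mg/kg figures as daily doses and assume a body weight of 50 to 100 kg; the documents state neither.
- Grade 2 row: 0.5 × 50 = 25 mg/day up to 1 × 100 = 100 mg/day.
- Grade 3/4/persistent Grade 2 row: 1 × 50 = 50 mg/day up to 2 × 100 = 200 mg/day.
- Weight at which the lowest dose passes the limit: 10 / 0.5 = 20 kg.

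On that reading every adult dose exceeds 10 mg/day. The exception in Section 6.6.3 is worded for irAEs, so a rise judged non-immune is not clearly covered by it.

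**5. Overlap inside Table 12.** Take a participant with Grade 1 creatinine at baseline who reaches Grade 2 in Cycle 1. Such a participant can be enrolled: Table 8 excludes serum creatinine only above 1.5 × ULN, which is the top of Grade 1, subject to its creatinine-clearance limits.
- First row: evaluate and repeat the laboratory tests; no prednisone.
- Grade 2 row: nephrology consult, evaluation, prednisone.

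On study drug the two rows give this participant essentially the same path: continue, recheck, and withhold if creatinine rises further. They differ on the consult and the steroid, and no precedence is stated.

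**6. Size.** Section 2.2.2 reports increased blood creatinine in 20.8% of 48 Phase 1 participants: 0.208 × 48 ≈ 10. This counts any grade and any cause, across all Phase 1 doses. The grade split is not given, so the number who would reach the prednisone rows cannot be derived.

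**The case against.** The best defense is that Table 12 is guidance to be read in context. Table 10 introduces it for immune-related events, Section 6.5.1 calls the irAE measures suggested and asks for other causes to be excluded, the lead-in wants work-up to start early, and both steroid cells list the nephrology consult and the evaluation before prednisone. An investigator could infer that the steroid is meant for suspected nephritis.

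That argument has force against stronger readings:

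- A reader might infer that prednisone is ordered for every Grade 2 or higher rise. The Cycle 1 row covers some Grade 2 rises without it, and the Table 10 scope and the evaluation bullets count against calling it an order.
- A reader might multiply 20.8% by the planned maximum of 304 (about 63) and call that the number exposed. The rate is for any grade and any cause and includes doses above this study's 400 mg BID maximum. Section 2.2.2 also says most adverse events were Grade 1 or 2, and the Grade 1 row has no steroid.
- A reader might calculate how small a transporter-only rise would carry a Grade 1 participant into Grade 2. The size of such a rise would be assumed, in Cycle 1 these participants also meet the row without prednisone, and Table 8's creatinine-clearance limits narrow who can enter near 1.5 × ULN.
- A reader might infer damage to the response endpoint or to the immune-event data. The documents do not show either. SAP Section 9.2.2 identifies potential irAEs from a sponsor-defined term list with clinical review, and states no steroid-use criterion.

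The defense does not settle the wording itself. The suggested status is attached to Table 10, the rule-out step governs classification and not when treatment starts, and the order of bullets sets no condition. Sites have to infer the scope, and the row overlap remains on any reading.

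**Conclusion.** The point holds as a contradiction in scope and trigger. The prednisone bullets in two rows of Table 12 are unconditional on cause. They do not fit the non-immune causes in the lead-in, the narrower citation in Table 10, the investigator discretion in Table 11, or the irAE-worded exception in Section 6.6.3. Separately, a Cycle 1 rise from Grade 1 to Grade 2 meets two rows that disagree on prednisone.

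The text comparison rests on no assumption. Only the comparison with 10 mg/day does: it takes the mg/kg figures as daily doses and the body weights as 50 to 100 kg. The number of participants affected is unknown. The SAP records early termination with minimal enrollment, so actual exposure will have been well below what the planned size would suggest. The correction is still worth making, because it bears on participant safety and costs little. No view is taken here on when a steroid should be given.

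**What to change.** Reconcile Table 12 with its lead-in, with Tables 10 and 11, and with Sections 6.5.1, 6.6.2.4 and 6.6.3. The revised text should state:

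1. for each of the two rows, whether the steroid bullet covers every creatinine rise or only those assessed as immune-related;
2. what happens to that bullet when the work-up finds OCT2 inhibition or another non-immune cause;
3. which row governs a Cycle 1 rise from Grade 1 at baseline to Grade 2;
4. which table governs a non-immune creatinine rise, and whether the Section 6.6 limits apply to steroids given for it.

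The content of each rule is the sponsor's clinical decision. The cost is a short wording change. It needs no new visits or tests, because the work-up for other causes is already listed.
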